CENTRAL COUNCIL FOR RESEARCH IN HOMOEOPATHY

DRUG PROVING

PROTOCOL

Generic Drug proving protocol for DP Program with sequential use of potencies in drug proving

Contents

STUDY SUMMARY.....	4
1. TITLE.....	6
2. TRIAL REGISTRATION.....	6
3. PROTOCOL VERSION.....	6
4. FUNDING.....	6
5. ROLES & RESPONSIBILITIES.....	6
6. INTRODUCTION & BACKGROUND.....	7
6.1 Background.....	7
6.2 Rationale.....	8
7. STUDY OBJECTIVE.....	8
8. STUDY DESIGN.....	8
9. METHODOLOGY.....	8
9.1 Study Settings.....	8
9.2 Eligibility criteria:.....	8
9.3 Sample size:.....	9
9.4 Proving Process.....	9
10. When and how to withdraw the provers.....	14
11. STUDY DURATION.....	15
12. PROVER PARTICIPATION TIMELINE.....	17
13. DATA COLLECTION AND MANAGEMENT.....	18
14. DATA ANALYSIS.....	20
14.1 Qualitative analysis:.....	20
14.2 Quantitative analysis - Dose- biological response relationship.....	21
15. ASSESSMENT OF SAFETY.....	21
15.1 Adverse events.....	21
15.2 Serious adverse event:.....	22
15.3 Causation likelihood.....	22
15.4 Un-blinding procedure.....	22
15.5 Follow-up of provers after AE (including SAE).....	23
15.6 Flow chart for Adverse event handling.....	24
16. RECORD KEEPING.....	25

17.	MONITORING.....	25
18.	PREMATURE TERMINATION OF STUDY.....	25
19.	ETHICAL CONSIDERATIONS.....	25
20.	TRAINING	26
21.	PROTOCOL AMENDMENTS	26
22.	PUBLICATION OF STUDY RESULTS:	26
23.	ACKNOWLEDGEMENT	27
24.	OPERATIONAL DEFINITIONS.....	27
25.	REFERENCES:.....	29

Study product, dose, route, regimen	
The homeopathic drug will be proved in ascending potencies. For each potency a batch will be prepared for the provers.
 
The provers will be enrolled following a pre-trial medical examination. Subsequent to a run-in period of 1 week the study medication will be prescribed to the prover.
 
Each batch of the drug will have 12 doses; each dose of 4 pills (Size 30). The prover will be asked to take 4 doses in a day (4 hourly) for 3 days from the prescribed batch of the coded drug. After the completion of the batch, one month washout period will be maintained in all provers, before the next batch is initiated.

Duration of administration	
3 days per batch (Maximum 12 doses).
 
Number of batches varying depending on the number of potencies in which the drug will be proved.

Intervention arms	IPS and Placebo
Blinding	
The study medication will be coded and blinding will be maintained during the study period with the PI at headquarters. The codes will be broken after the study period at the research centre is completed and data will be analyzed.

Study course and data collection	
An analysis to extract dependable homeopathic prescribing indications from a drug proving is required to contain the following dimensions:
 
 • 1st dimension: All symptoms occurring during the Proving • 2nd dimension: Proving symptoms with relative characterizing assessment • 3rd dimension: Characteristic symptoms (a highly individualized subset)
Data analysis	
The proving symptoms will be identified and segregated from the symptoms produced in placebo group. The proving symptoms will form the drug pathogenesis.

1. TITLE

Homoeopathic drug proving: Randomized double blind placebo controlled trial

2. TRIAL REGISTRATION

The trial will be registered on CTRI

3. PROTOCOL VERSION

Version 6 October 2014

4. FUNDING

The study will be conducted by the Central Council for Research in Homoeopathy (CCRH), Department of AYUSH, Ministry of Health and family welfare at its identified research centres. The study will be fully funded by CCRH.

5. ROLES & RESPONSIBILITIES

5.1 Regulatory Committees:

At the level of CCRH headquarters:

The protocol will be placed for approval of:

1. Ethical committee of CCRH
2. Special Committee for Drug Proving of CCRH
3. Scientific Advisory Committee of CCRH

A 'data safety management board' may be constituted by the Director General CCRH for proving of new/non-pharmacopoeial drugs, responsible for supervision of drug proving of new/non-pharmacopoeial drugs.

At each study centre

A Drug proving committee will be formed at each research centre involving faculty from the colleges and scientists at the research centre. The committee shall comprise of 5-6 members responsible for conduct of the study, enrollment & safety of participants, data collection & data integrity, etc.

5.2 Study Team

At CCRH/Headquarters

Principal Investigator - Director General, Central Council for Research in Homoeopathy, New Delhi

Coordinator & Co-Investigator(s)-Designated officers of CCRH

At Research centre (Centre of CCRH functioning in Homoeopathic Medical College premises)

Site investigator - Designated officer(s) of CCRH responsible for drug proving program

Site co-investigator(s) - Designated officer(s) of homoeopathic college where the proving program is being conducted

5.4 Compliance statement

The study will be conducted in accordance with this protocol and will comply with all the requirements regarding the obligations of investigators and all other pertinent requirements

1. Drugs and Cosmetic Act 1940 & Rules 1945 of Government of India^[1]
2. Good Clinical Practice^[2]
3. Declaration of Helsinki^[3]

6. INTRODUCTION & BACKGROUND

6.1 Background

'Drug Proving' is a method, unique to Homoeopathy where the pathogenesis of a drug is evolved through its trials on apparently Healthy Human Volunteers (Provers). Provings are an important part of homoeopathic theory and a mainstay of its practice since the first proving of *Cinchona officinalis* by [name] in 1790^[4]. Based on the pathogenesis, a drug picture is evolved, on the basis of which prescription is made. It provides a necessary tool to find the most appropriate remedy for the patient^[5].

[name], also called the "Father of Experimental Pharmacology" for developing a new principle for ascertaining the curative power of medicinal substances, laid the foundation of drug proving and detailed the process. He tested 99 drugs on himself, his family and his colleagues, in order to discover the effects of drugs on healthy individuals. In this context he stressed the need of proving drugs on healthy persons, which is the best way to obtain an unadulterated picture of the drug. In his 'Organon of Medicine' (Aphorism 105 –145)^[6], Hahnemann gave detailed instructions regarding the method of homoeopathic drug proving in healthy subjects.

Over the years, provings have been conducted by a number of authorities, most of whom have devised their own methodologies. Over the years, the term homoeopathic pathogenetic trials (HPT) is also frequently used for drug proving and these are considered to be clinical trials^[7,8]. Drugs and Cosmetics Rules 1945 (Rule 122 DAA inserted in 2005) of the Government of India^[1] defines clinical trial as "a systematic study of new drug(s) in human subjects(s) to generate data for discovering and/or verifying the clinical pharmacological (including pharmacodynamic and pharmacokinetic) and/or adverse effects with the objective of determining safety and/or efficacy of the new drug. Proving of drug substances in homoeopathy is done to identify their therapeutic potential and is primarily a study of action of these drugs on healthy human beings. As such these studies fall under the purview of clinical trials, and therefore must conform to the GCP guidelines^[2] issued by the regulatory authorities in the country. HPT trials are similar to Phase I clinical trials with a major difference that the aim of the trial is not to elicit the therapeutic dosage (bio-availability) or pharmacokinetic response, but to elicit the pharmaco-dynamic (biological response) to ultra high diluted, non-toxic doses of the intervention and are observed in terms of symptoms which are temporary and disappear after stoppage of intervention.

Drug Proving was formally initiated by the Homoeopathic Research Committee (formed in 1963). Since inception of the CCRH, the proving program has been continuing and is one of the most important research programs of the Council. The Council has over the years, devised a methodology for drug proving as detailed in the protocol.

The drug proving program of the Council is conducted in coordination with homoeopathic medical colleges and a large number of provers are students of these colleges, apart from provers of non-homoeopathic background. In each program, it is attempted to include volunteers from non-homoeopathy background also, apart from the students. As such the proving team comprises of scientists from the institute/unit of the Council and academicians from the homoeopathic colleges.

6.2 Rationale

The symptoms produced by the healthy provers form the basis of developing a homoeopathic materia medica which identifies the symptom indications, on which the drug can be prescribed to the patients. As such drug proving is the first step for development of a symptom picture of a homoeopathic medicine. The process needs to be standardized, so that the likelihood of reproducibility increases and the reliability of symptoms so identified increases. The symptomatology so identified will construct an authentic homoeopathic material medica and can be verified clinically based upon the "Laws of Similar". The symptoms identified in drug proving will form the baseline data for subsequent verification and validation studies.

7. STUDY OBJECTIVE

To identify pathogenetic effects of a homoeopathically prepared drug substance (Investigational proving substance or IPS) on healthy human beings

8. STUDY DESIGN

The study will be prospective, parallel arm, randomized, placebo-controlled study.

Study Type:	Interventional
Allocation:	Randomized
Verum/placebo ratio(%):	Unbalanced (70/30)
Masking:	Double blind
Comparator:	Placebo
Endpoint Classification:	Disappearance of symptoms appearing during proving and subsequent symptom free period of 30 days.

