- Since the symptoms appearing during proving are transient in nature, it is not expected that the symptoms will persist for long. During the course of proving, the prover is referred to medical expert/consultant for examination & for specific laboratory investigation(s), if needed, to rule out any pathological cause for appearance of new symptom(s)/sign(s) in case symptoms persist for more than 3 days or is distressing to the prover. Laboratory tests are also performed to facilitate observation of any correlation between the subjective and objective changes during the course of proving. The opinion of the experts is also taken, on the appearance of new sign(s)/symptom(s), wherever needed.
- Photos of objective findings (e.g. skin eruptions, swellings, etc.) will also be taken and to be kept along with the prover record.

Observation period: During the period that the symptoms persist, the prover will be kept under observation of the investigator. The prover will be instructed to report (preferably on a personal visit or telephonically) to the investigator daily (or more frequently) for as long as the symptoms persist.

Washout period: Subsequent to disappearance of the symptoms, a period of 30 days will be kept as washout period. The prover will report to the investigator once a week (or earlier in case of

development of any symptoms or any change in health status) during which the investigator will interrogate and examine the prover to identify any change in health status. The prover (in form E) and the investigator (in form F&G) will be expected to complete the details of the symptoms as mentioned in section 9.4.16.

In case of appearance of symptoms during this period, the prover will be kept under observation of the investigator. The prover will be instructed to report (preferably on a personal visit or telephonically) to the investigator daily (or more frequently) for as long as the symptoms persist. After symptoms have disappeared, a period of further 30 days symptom free period will be maintained as a wash out period before the start of the next batch of study medication.

B. If no sign(s)/symptoms(s) appear:

Prover may not develop any sign/symptom till the completion of 12 doses. In such a case, the prover notes down as 'No Symptom' with date and time of intake of the respective dose of the drug, verified by the investigator.

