9.4.19 Post –Trial (Terminal) Medical examination (Form D)

After all the batches of the study medication are consumed and a subsequent washout period of 30 days, the provers are examined again as in the PME, and the process is called 'Terminal Medical Examination' (TME). The TME must be completed within two weeks after completion of the washout period.

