11. STUDY DURATION

The duration of proving for each prover will depend upon the symptoms produced and the subsequent wash out periods, needed, before subsequent doses can be given.

Expected duration for study

11.1 At research centre level:

- Prover screening: 1 week
- PME: 2 weeks (for completion of PME at a centre)
- Run in period (till receipt of IP batches): 2 weeks (to a maximum of 4 weeks)
- Administration of first batch: 3 days
- First washout period: 30 days (+ days for which symptoms persisted)
- Administration of second batch: 3 days
- Second washout period: 30 days (+ days for which symptoms persisted)
- Administration of third batch: 3 days
- Third washout period: 30 days (+ days for which symptoms persisted)
- TME: 1 week (to 2 weeks for completion of PME at a centre)

[figure not shown]
In case where no symptoms appear, a symptom free period of 30 days is maintained. In case(s) where symptoms appear, the observation period for each prover will vary depending on the duration for which the proving symptoms persist, subsequently followed by a 30 day symptom free washout period. (See section 9.4.17 for details)

As such for proving of each IPS an approximate duration of 7 months to 12 months is needed.

11.2 At Headquarters level, the study duration will include:

- Protocol preparation, regulatory approval, pretrial preparations: 2 months
- PME Assessment, randomization and allotment of batches, preparation of batches: 2 weeks (to a maximum of 3 weeks)
- Monitoring and supervision of study at research centre level: 7 months (to approx. 12 months)
- Data compilation & de-coding & analysis: 2 months
- Report preparation: 1 month

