14.2 Quantitative analysis - Dose- biological response relationship

The principal analyses will employ the 'intention-to-treat' approach and will include all randomized participants in their randomly assigned groups. Comparison of the baseline characteristics among the two groups will use standard parametric & nonparametric statistical techniques.

The overall incidence of proving symptoms in each trial will be calculated by dividing the number of volunteers who had at least one reported proving symptom (pathogenetic effect) by the total number of volunteers taking the IPS (not on placebo)^[7].

The incidence of proving symptoms per volunteer is defined as the total number of findings claimed in the trial divided by the total number of subjects using the IPS (not placebo)^[7].

One proving symptom will be counted as a piece of information which could be included in a homeopathic repertory as an independent subheading. For instance, boring headache ameliorated by pressure is counted as one claim ^[7].

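### The only endpoint named (Section 8) is the washout rule: completers in both arms meet it by procedure, so it does not measure the symptom occurrence that Sections 7, 13 and 14 concern

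*Protocol*

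**What the plan says.** The design table in Section 8 gives the endpoint as "Disappearance of symptoms appearing during proving and subsequent symptom free period of 30 days". No other section names an endpoint.

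The objective in Section 7 is different: "To identify pathogenetic effects of a homoeopathically prepared drug substance" in healthy people. It concerns symptoms appearing, not resolving.

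The follow-up rules use almost the same words as the endpoint:

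- Section 9.4.17, prover with symptoms: "Subsequent to disappearance of the symptoms, a period of 30 days will be kept as washout period".
- Section 9.4.17, symptoms appearing during washout: "After symptoms have disappeared, a period of further 30 days symptom free period will be maintained as a wash out period".
- Section 11.1, prover without symptoms: "In case where no symptoms appear, a symptom free period of 30 days is maintained".
- Section 9.4.19, terminal examination: "After all the batches of the study medication are consumed and a subsequent washout period of 30 days, the provers are examined again".

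The analysis sections deal with occurrence. Section 13.2 defines a proving symptom, 13.4 removes symptoms identical under drug and placebo, and 14.1 selects and grades symptoms. Section 14.2 calculates an overall incidence by "dividing the number of volunteers who had at least one reported proving symptom (pathogenetic effect) by the total number of volunteers taking the IPS", and states that those on placebo are not counted in that denominator.

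**The concern.** An endpoint in a randomised placebo-controlled trial should be a result that the treatment can change. The Section 8 entry is instead a condition that a prover must satisfy before the next batch or the terminal examination. Satisfying it shows that the procedure was followed. It does not show whether the drug produced symptoms.

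Two things are at stake. The stated endpoint, the objective and the analysis do not describe the same quantity, so a reader cannot tell which result the trial is meant to deliver. The placebo arm also has no stated numerical role: the endpoint does not separate the arms among completers, and the incidences in 14.2 leave the placebo group out. Because this is a generic protocol for a programme of provings, the mismatch can recur with each drug.

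**Working it through.** **Inputs.** Allocation 70/30 (Section 8). Minimum 30 participants, 20% dropout, 40 to enrol (Section 9.3). Follow-up rules from 9.4.17, 9.4.19 and 11.1. The protocol gives no rate, effect size or power for the endpoint, so there is no endpoint figure to reproduce. The enrolment figure reproduces closely: 30 / (1 − 0.20) = 37.5, so 38, against the stated 40. It is used here only for group sizes, taking 70/30 as exact:

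- N = 30: 30 × 0.70 = 21 verum, 9 placebo.
- N = 40: 40 × 0.70 = 28 verum, 12 placebo.

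**Step 1: who meets the endpoint.**

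| Prover | What must happen before the next stage | Endpoint met? |
|---|---|---|
| Symptoms after a batch | They disappear, then 30 days | Yes |
| Symptoms return in washout | They disappear, then a further 30 symptom-free days | Yes |
| No symptoms | 30 symptom-free days (11.1) | Only the 30-day part; nothing to disappear |
| Withdrawn | Leaves the sequence | Not necessarily |

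The rows apply equally to verum and placebo. Section 9.4.19 alone does not say that the last washout must be symptom-free. Section 11.1 supplies that.

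**Step 2: completers.** Counting never-symptomatic provers as meeting the endpoint, attainment is 21/21 against 9/9, or 28/28 against 12/12 if all 40 complete. The difference is 0 and Fisher's exact p = 1.0.

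Two extreme cases among the 21 verum completers show the consequence. If none has a proving symptom, the endpoint is 21/21 and the incidence in 14.2 is 0/21. If all have one, the endpoint is still 21/21 and the incidence is 21/21. The endpoint does not move and the incidence does.

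**Step 3: all randomised.** Count a non-completer as not meeting the endpoint (an assumption, since Section 8 is silent). Attainment in each arm then equals its completion proportion, and the difference between arms is the difference in completion. At the planned dropout, 40 × 0.20 = 8 leave and 32/40 = 80% attain. How those 8 fall is not known, so the possibilities run as follows:

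- 6 verum, 2 placebo: 22/28 = 78.6% against 10/12 = 83.3%, difference −4.8 points.
- All 8 verum: 20/28 = 71.4% against 12/12 = 100%, difference −28.6 points.
- All 8 placebo: 28/28 = 100% against 4/12 = 33.3%, difference +66.7 points.

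These differences come from who left.

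**Step 4: would an occurrence outcome do better?** It can separate the arms, though not precisely at this size. With 21 against 9, a two-sided 5% Fisher test and assumed incidences of 30% on placebo and 60% on verum, the probability of rejection is 0.288. Across assumed placebo incidences of 20% to 50% and differences of 20 to 50 points (verum below 100%), it runs from 0.121 to 0.808. For the Section 8 endpoint among completers it is 0.

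**The case against.** The strongest reply is that the entry is a misplaced follow-up rule and nothing more. The protocol never calls it primary, bases no sample size on it and does not analyse it. The outcomes that matter are in 13.2, 13.4, 14.1 and 14.2. Section 14.1 says there is no efficacy measure and that evaluation is qualitative, so a between-arm proportion would not identify which symptoms belong to the drug. Most of this stands, and it sets the scope of the point: the entry is mislabelled and must be brought into line with Sections 7, 13 and 14. It does not remove the point, because the only stated endpoint remains one that the analysis does not use.

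A reader might infer more than the documents support:

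- **That the arms cannot differ whatever the drug does.** This holds only for completers. Section 14.2 makes the principal analyses intention-to-treat. Under 15.1 a symptom that is longer or more severe than expected can be an adverse event, and 15.5 withdraws provers with one. A drug causing such symptoms could lower attainment in the verum arm.
- **That the trial registry would carry this endpoint.** The protocol says the trial will be registered, but not which text fills the outcome field.
- **That the outcome is left open until decoding.** Sections 13.2 and 14.2 fix the definition and counting unit in advance, and 13.3 puts prover-wise symptom entry before un-blinding. Matching and compilation do follow decoding, but the Section 8 entry does not cause that.
- **That 14.2 already contains the replacement.** It does not. Its denominators are IPS takers, and no placebo rate is calculated.

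**Conclusion.** The point holds in limited form. The sole named endpoint restates the washout rule. Among completers it is met in both arms by procedure: 21/21 against 9/9 at the minimum size, a difference of 0. This assumes that the follow-up rules are kept and that never-symptomatic provers count as meeting it through the 30-day part. Among all randomised provers it would differ mainly through withdrawal, which may be linked to the drug through adverse events but is not the occurrence of proving symptoms.

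The endpoint therefore neither measures the objective nor matches the analysis. The protocol does not lack relevant measures. It names the wrong one, and the incidences it does define have no placebo counterpart. This should be corrected, but it does not invalidate data collection.

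**What to change.** 1. **Section 8.** Replace the endpoint entry with a symptom-occurrence outcome, such as the proportion of provers with at least one proving symptom under the 13.2 definition, classified before un-blinding. The site classification in 9.4.16 is already made blind, so the count should use it as it stands before the removal step in 13.4.
2. **Sections 9.4.17 and 11.1.** Keep the present endpoint text only here, as the follow-up rule.
3. **Section 14.2.** Calculate the same incidence in the placebo group and compare the randomised groups. Report the placebo batch of verum provers separately, and state which batches enter each count so that the groups are compared over the same number.
4. **Section 14.1.** Leave the qualitative selection and grading as they are. They still determine which symptoms enter the drug picture.

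The cost is one table entry and a small amendment to 14.2. No new data are needed, because Forms E and F already record symptoms by prover and batch in both arms. Given the group sizes, the comparison is better reported as a difference with its uncertainty than relied on as a test.
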